4.7.2 Clinical studies of VRC01LS

VRC01LS is initially being evaluated in the VRC 606 study: “*A Phase 1, Dose-Escalation Study of the Safety and Pharmacokinetics of a Human Monoclonal Antibody, VRC-HIVMAB080-00-AB (VRC01LS), and VRC-HIVMAB060-00-AB (VRC-01), Administered Intravenously or Subcutaneously to Healthy Adults*”.

VRC 606 is the first study of the VRC-HIVMAB080-00-AB (VRC01LS) monoclonal antibody (mAb) in healthy adults. It is a dose-escalation study to examine safety, tolerability, dose, and pharmacokinetics of VRC01LS. There are 4 open-label, dose escalation groups (Groups 1-4) to assess VRC01LS administered IV and SC once per subject and 2 open-label groups (Groups 5 and 6) to assess VRC01LS at 5 mg/kg SC or at 20 mg/kg IV administered every 12 weeks for a total of 3 administrations per subject. Two additional open-label groups (Groups 7 and 8) assess VRC01 at 5 mg/kg SC or at 20 mg/kg IV administered every 4 weeks for a total of 2 administrations per subject. The study schema is depicted in [Table 4-11](#).

Table 4-11: VRC 606 Study Schema

Group	Subjects	Product	Administration Schedule			
			Day 0	Week 4	Week 12	Week 24
1	3	VRC01LS	5 mg/kg IV			
2	3	VRC01LS	5 mg/kg SC			
3	3	VRC01LS	20 mg/kg IV			
4	5	VRC01LS	40 mg/kg IV			
5	15	VRC01LS	5 mg/kg SC		5 mg/kg SC	5 mg/kg SC
6	10	VRC01LS	20 mg/kg IV		20 mg/kg IV	20 mg/kg IV
7	5	VRC01	5 mg/kg SC	5 mg/kg SC		
8	5	VRC01	20 mg/kg IV	20 mg/kg IV		
Total*	49					

*Enrollment up to a total of 60 subjects is permitted in case there are subjects who do not complete the schedule, if additional PK evaluations are needed, or if an enrollment of additional subjects is necessary for safety evaluations (Section 4.3).

The first product administration occurred on November 18, 2015 and the study is ongoing. As of July 17, 2017, 39 people have received VRC01LS in three dose groups: 5mg/kg IV and SQ, 20mg/kg IV, and 40mg/kg IV, and 25 participants have completed study participation. No dose limiting toxicities have occurred. There have been no severe adverse events. One participant who received subcutaneous product administration experienced moderate local reactogenicity (pain/tenderness at the injection site). 29 of 39 (74.4%) participants have had one or more unsolicited AEs, with maximum severity of Grade 1 for 18 participants and Grade 2 for 11 participants. Six AEs were assessed as related to study product: two instances of Grade 1 diarrhea, one instance of Grade 1 dizziness, one Grade 1 injection site reaction, and two instances of Grade 1 AST elevation.

VRC01LS administrations have been generally well tolerated.

4.8 Potential risks of study products and administration

In a preclinical study performed in rats, there was a small dose-dependent, but transient, increase in AST and ALP, but not in ALT following IV administration. In rats, there were no histopathology findings following IV administration.

Thus far in VRC 601, VRC 602, and HVTN 104 there have been no safety concerns, including no SAEs deemed related to study product. Administration of any mAb may have a risk of immune reactions such as acute anaphylaxis, serum sickness, and the generation of auto-reactive antibodies; however, these reactions are rare and more often associated with mAbs targeted to human proteins or with the use of murine mAbs, which would have a risk of generating human anti-mouse antibodies (58). In this regard, as VRC01 is targeted to a viral antigen and is a human mAb, it is expected to have a low risk of such side effects.

Typically, the side effects of mAbs are mild but may include fever, flushing, chills, rigors, nausea, vomiting, pain, headache, dizziness, shortness of breath, bronchospasm, hypotension, hypertension, pruritus, rash, urticaria, angioedema, diarrhea, tachycardia, chest pain, or reactions at injection site (pain, redness, bruising, swelling). Clinical use of mAbs that are targeted to cytokines or antigens associated with human cells may be associated with an increased risk of infections (58); however, this is not expected to be a risk for a mAb targeted to a viral antigen.

It is known from published experience with human mAbs directed against the cell surface targets on lymphocytes that infusion of a mAb may be associated with cytokine release, causing a reaction known as “cytokine release syndrome” (59). “Cytokine release syndrome” and other immune reactions such as tumor lysis syndrome have been observed with administration of chimeric and humanized mAbs (58). Most infusion-related events occur within the first 24 hours after beginning administration. Specifically, with regard to cytokine release syndrome reactions, these most commonly occur within the first few hours of beginning the infusion and are more common with the first mAb infusion received. This is

because the cytokine release is associated with lysis of the cells targeted by the mAb and the burden of target cells is greatest at the time of the first mAb treatment. With licensed therapeutic mAbs, cytokine release syndrome is managed by temporarily stopping the infusion, administering histamine blockers, and restarting the infusion at a slower rate (60). Severe reactions such as anaphylaxis, angioedema, bronchospasm, hypotension, and hypoxia are infrequent and more often associated with mAbs targeted to human proteins or with a non-human mAb, such as a murine mAb (58). Most infusion-related events occur within the first 24 hours after beginning administration.

Delayed allergic reactions to a mAb may include a serum sickness type of reaction, which is characterized by urticaria, fever, lymph node enlargement, and joint pains. These symptoms may not appear until several days after exposure to the mAb and are noted to be more common with chimeric types of mAb (58). Serum sickness has not been described with administration of licensed, fully human mAbs.

There are several FDA-licensed mAbs for which reactions related to the rate of infusion have been described. Some symptoms may be treated by slowing or stopping the infusion.

Other side effects of licensed mAbs include infections, thrombocytopenia, autoimmune diseases, cancer, dermatitis, and cardiotoxicity (58).

The HVTN laboratory tested plasma from HIV-uninfected individuals that was spiked with VRC01 in a range of concentrations that encompasses those likely to be observed in this clinical trial. VRC01 did not cause a reactive test result using several standard antibody-based HIV-1/2 diagnostic tests. However, since VRC01 is an antibody to an HIV protein, so, it may be theoretically possible for a standard antibody-based HIV diagnostic test to detect VRC01 for a short time period postinfusion or postinjection. However, in practice this has not been observed in clinical studies with VRC01 to date.

Risks of Blood Drawing: Blood drawing may cause pain and bruising and may, infrequently, cause a feeling of lightheadedness or fainting. Rarely, it may cause infection at the site where the blood is taken. Problems from use of an IV for blood drawing are generally mild and may include pain, bruising, minor swelling or bleeding at the IV site and, rarely, infection, vein inflammation (phlebitis), or blood clot.

Risks of IV Infusion: The placement of an IV catheter can allow for the development of bacteremia because of the contact between the catheter and unsterile skin during insertion. Risk of infection from IV infusion will be minimized through careful decontamination of skin prior to catheter placement and through the use of infection control practices during infusion. The risk of product contamination will be minimized through the use of aseptic techniques during product preparation and administration.

Risk of biopsy collections: Possible complications of biopsies are bleeding and infection. These complications are rare and risks of these complications will be minimized by careful hemostasis by the clinicians and detailed education of the participants to report bleeding and/or fever after the procedures. As biopsies create breaches in mucosal integrity, the risk of HIV infection - if exposed - is potentially increased during wound healing. Therefore (and to allow for undisturbed wound healing) an abstinence period is required of the participants (see Section 7.1, Criterion 26 and Section 9.6) after each biopsy. Healing of the superficial wounds in mucous membranes caused by these shallow, small (~2-4mm) biopsies is rapid; by 5-14 days, healing is expected to be complete (61). In the proposed schedule, a minimum of 28 days between biopsy collections will be adhered to, and repetitious biopsies are not assumed to increase the risk as compared to a single biopsy. More than 150 clinic visits involving multiple biopsy collections have been performed at the Seattle HIV Vaccine Trials Unit in the past two years and thus far not a single complication has occurred. In the Cape Town Area Control (CTAC) study, seven female participants were enrolled for the collection of cervical and vaginal samples. Up to five biopsies (cervical, vaginal or a combination of both) were collected at a single visit. Twelve (male and female) participants were enrolled for rectal biopsy collections. To date, two participants underwent first, an anoscopy (with collection of five rectal biopsies), and then a second collection via flexible sigmoidoscopy 10 weeks later (with collection of 5 rectal biopsies and 19 colonic biopsies). Nine participants have undergone one biopsy collection via rigid sigmoidoscopy (with collection of 5 rectal biopsies and 19 colonic biopsies). One participant has undergone two rigid sigmoidoscopies 10 weeks apart (with collection of 5 rectal biopsies and 19 colonic biopsies). All participants were HIV negative at enrollment and have remained HIV negative 1 year post-biopsy collection visit.

5.1 Primary objectives and endpoints

Primary objective 1

- To evaluate the safety and tolerability of VRC01/VRC01LS mAb administered through IV infusion

Primary endpoint 1

- Local and systemic reactogenicity, laboratory measures of safety, AEs, SAEs, and rates of discontinuation

Primary objective 2

- For each sex at birth, to evaluate the pharmacokinetics of VRC01 in serum versus mucosa in each mucosal compartment

Primary endpoints 2 (Groups 1 & 2 & 4)

- Serum concentration of VRC01 out to Month 6 after the last infusion
- Levels of VRC01 in genital and rectal secretions, as well as cervical, vaginal, and rectal tissues at the collection timepoints

5.2 Secondary objectives and endpoints

Secondary objective 1

- To evaluate the ability of the *in vivo*-infused VRC01/VRC01LS antibodies to inhibit HIV-1 infection in tissue explants

Secondary endpoint 1

- *Ex vivo* inhibition of HIV-1 infectivity in tissue biopsies in Groups 1 - 3

5.3 Exploratory objectives

Exploratory objective 1:

For each sex at birth, to evaluate the pharmacokinetics of VRC01LS in serum versus mucosa in each mucosal compartment

Exploratory objective 2:

To evaluate the levels of VRC01LS in serum, mucosal secretions, and mucosal tissues and those of VRC01 at the 30 mg/kg dose level.

Exploratory objective 3:

To evaluate the tissue distribution of VRC01/VRC01LS in mucosal biopsies.

Exploratory objective 4:

To compare the levels and functionality of VRC01/VRC01LS in mucosal secretions and tissues between the cervical, vaginal, and rectal compartments from the same participant.

Exploratory objective 5:

To assess the relationship between inflammation in mucosal biopsies and levels of antibody in these tissues and related secretions.

Exploratory objective 6:

To assess the acceptability and tolerability of repeat mucosal sampling, including secretions and biopsies, for application in future studies.

Exploratory objective 7:

To assess the relationship between Fc receptor genotypes and VRC01/VRC01LS pharmacokinetics and/or *ex vivo* infectivity of biopsies.

Exploratory objective 8:

To further evaluate the retention of functional characteristics of *in vivo*-infused VRC01/VRC01LS in each group, additional assays may be performed, including on samples from other timepoints.

Exploratory objective 9:

To conduct analyses related to furthering the understanding of HIV, immunology, vaccines, antibody mediated prevention, and clinical trial conduct.

6 Statistical considerations

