9.6 Mucosal sampling

Mucosal secretion and biopsy samples will be collected at the timepoints indicated in [Appendix L](#), [Appendix M](#), [Appendix N](#), and [Appendix O](#). All participants in this trial will have consented to mucosal specimen collections. Participants born male will provide semen, rectal fluids, and rectal biopsies. Participants born female will provide cervicovaginal fluids, as well as cervical and vaginal biopsies. At the Seattle CRS, female participants will also provide rectal fluids and rectal biopsies, if they agree to do so. Small (~2-4 mm) tissue biopsies are obtained from the vagina and cervix using a speculum and from the rectum by anoscopy by experienced clinicians. The number of biopsies per mucosal compartment and visit is described in detail in [Table 9-1](#) and [Table 9-2](#), and also outlined in [Appendix H](#), [Appendix I](#), [Appendix J](#), and [Appendix K](#), however fewer samples may be taken based on the judgment of the performing clinician. If a female participant is no longer willing to provide cervicovaginal specimens, a switch to the rectal compartment is possible. During the trial, a participant may decline all or some of the mucosal biopsies or secretion collections, but they should be encouraged to continue with any collections that they deem acceptable until the end of the trial.

Table 9-1 Mucosal biopsy collection schedule for Groups 1-3

Tissue	Function	Visit 2 (Baseline)	Visit 14 (Month 6)	Visit 15 (Month 7)	Visit 16 (Month 9)	Visit 17 (Month 12)	Visit 18** (Month 15)	Visit 19** (Month 18)
Rectal # of Bx and Use	Ab levels	1	1	1	1	1	1	1
	IHC	1	1	1	1	1	1	1
	Infectivity	3	3	3	3	3	3	3
	Total = 35*/25	5	5	5	5	5	5	5
Ectocervical # of Bx and Use	Ab levels	1	1	1	1	1	1	(1)***
	IHC	1	1	1	1	1	1	(1)***
	Infectivity	2	2	-	-	-	-	-
	Total = 16*/14	4	4	2	2	2	2	(2)***
Vaginal # of Bx and Use	Ab levels	1	1	1	1	1	1	(1)***
	IHC	1	1	1	1	1	1	(1)***
	Infectivity	3	3	3	3	(3)***	(2-3)***	(2-3)***
	Total = 24*/22	5	5	5	5	2 [(5)***]	2 [(4-5)***]	(2-5)***

* Number of samples refers to Group 3

** Visits only apply to group 3

*** These samples will only be collected if the participant has missed prior collection visit(s), in order to maintain the total number of biopsies indicated in the "Function" column.

Table 9-2 Mucosal biopsy collection schedule for Groups 4-5

Tissue	Function	Visit 4 (0 mo)	Visit 5 (1 mo)	Visit 9 (3 mo)	Visit 12 (4.5 mo)	Visit 14 (6 mo)	Visit 16** (9 mo)	Visit 17** (12 mo)

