#### 3.3. Exploratory objectives and endpoints

*Exploratory objective 1:*

- For each sex at birth, to evaluate the pharmacokinetics of VRC01LS in serum versus mucosa in each mucosal compartment.

*Exploratory objective 2:*

- To evaluate the levels of VRC01LS in serum, mucosal secretions, and mucosal tissues and those of VRC01 at the 30 mg/kg dose level.

*Exploratory objective 3:*

- To evaluate the tissue distribution of VRC01/VRC01LS in mucosal biopsies.

*Exploratory objective 4:*

- To compare the levels and functionality of VRC01/VRC01LS in mucosal secretions and tissues between the cervical, vaginal, and rectal compartments from the same participant.

*Exploratory objective 5:*

- To assess the relationship between inflammation in mucosal biopsies and levels of antibody in these tissues and related secretions.

*Exploratory objective 6:*

- To assess the acceptability and tolerability of repeat mucosal sampling, including secretions and biopsies, for application in future studies.

*Exploratory objective 7:*

- To assess the relationship between Fc receptor genotypes and VRC01/VRC01LS pharmacokinetics and/or ex vivo infectivity of biopsies.

*Exploratory objective 8:*

- To further evaluate the retention of functional characteristics of in vivo–infused VRC01/VRC01LS in each group, additional assays may be performed, including on samples from other timepoints.

*Exploratory objective 9:*

- To conduct analyses related to furthering the understanding of HIV, immunology, vaccines, antibody mediated prevention, and clinical trial conduct.

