For each tissue biopsy type, graphical and tabular summaries of the distributions of *ex vivo* inhibition of HIV-1 infectivity summarized by AUC (or other measurements) will be made for each challenge virus, treatment arm, and timepoint. Comparisons between groups 1-3 will be stratified by site. The difference between treatment arms at a specific timepoint will be tested with an extension of the nonparametric Wilcoxon rank sum test for two-way analysis (i.e., the Van Elteren test) if the data are not normally distributed and with a stratified 2-sample t-test if the data appear to be normally distributed. An appropriate data transformation may be applied to better satisfy assumptions of symmetry and homoscedasticity (constant variance). The same testing

approaches will be used to compare infectivity between male rectal vs. female cervical/vaginal, between male rectal vs. female rectal, and between female cervical vs. female vaginal at each time-point, stratified by dose groups.

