### **Singulex assay for mucosal VRC01/VRC01LS Levels**

VRC01/LS concentrations will be calibrated via a 5PL model of the standard samples on the same plate. The machine Erenna detects single molecules of VRC01/VRC01LS as photons over a read time. Each measurement of photons above a threshold is considered a detected event and the sum of all photons from these events over the read time (i.e. signal intensity) is called the event photon (EP) measurement for the sample or standard. The EP curve of the VRC01/LS standard will be used to calibrate the VRC01/VRC01LS concentrations in mucosal and serum samples. The lower limit of quantitation (LLoQ) of each run is defined by the lowest standard maintaining less than or equal to 20% coefficient of variation (CV). The estimation of the standard curve and the calibration of study samples will be carried out using the nCal package in R (Fong et al., Biometrics, 2012; Fong et al., Bioinformatics, 2013).

Graphical and tabular summaries of the distributions of VRC01/LS mucosal levels normalized by total IgG/protein, as well as levels data without normalization will be made for each biopsy type, treatment arm, and time point. Correlation plots will be generated between different sample types.

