## 10.2. Mucosal VRC01/LS Level

### 10.2.1. List of Tables

- Summary statistics (i.e., min, mean, median, max, standard deviation, IQR) of VRC01/LS concentration normalized by total IgG and protein, by tissue type, visit, and treatment arm.
- Summary statistics (i.e., min, mean, median, max, standard deviation, IQR) of total IgG and protein, by tissue type, visit, and treatment arm.
- Summary statistics (i.e., min, mean, median, max, standard deviation, IQR) of VRC01/LS concentration without normalization, by tissue type, visit, and treatment arm.

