### 10.2.2. List of Graphs

- Boxplots of baseline mucosal level normalized by total IgG, by sex at birth, tissue type, and treatment arm
- Boxplots of baseline mucosal level normalized by protein, by sex at birth, tissue type, and treatment arm
- Boxplots of baseline mucosal level without normalization, by sex at birth, tissue type, and treatment arm
- Lineplots of baseline and post-infusion mucosal level normalized by total IgG, by sex at birth, tissue type, and treatment arm
- Lineplots of baseline and post-infusion mucosal level normalized by protein, by sex at birth, tissue type, and treatment arm
- Lineplots of baseline and post-infusion mucosal level without normalization, by sex at birth, tissue type, and treatment arm

- Scatterplots of correlation as following:

Cervicovaginal secretions to Cervical homogenates

Cervicovaginal secretions to Vaginal homogenates

Blood to Cervical homogenates

Blood to Vaginal homogenates

Blood to Cervicovaginal secretions

Rectal secretions to rectal homogenates

Rectal secretions to Semen

Rectal secretions to blood

Rectal homogenates to Semen

Rectal homogenates to blood

Rectal homogenates to Cervical lysates

Rectal homogenates to vaginal lysates

Rectal homogenates to cervicovaginal secretions

Rectal secretion to Cervical lysates

Rectal secretion to vaginal lysates

Rectal secretion to cervicovaginal secretions

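### For exploratory objective 4, the SAP lists no numerical within-participant contrast of antibody levels between mucosal compartments

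*Protocol*

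**What the plan says.** Protocol 5.3 sets the objective as "To compare the levels and functionality of VRC01/VRC01LS in mucosal secretions and tissues between the cervical, vaginal, and rectal compartments from the same participant". SAP 3.3 restates it, including the phrase "between the cervical, vaginal, and rectal compartments from the same participant". It names two quantities, levels and functionality, and asks for both within the same person.

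For functionality, SAP 8.5.2 (TLA assay) plans tests between tissues, ending with "and between female cervical vs. female vaginal at each time-point, stratified by dose groups". SAP 10.1.1 lists tables of comparisons between tissue types, and one item asks for both comparisons and correlations across the three female tissues.

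For levels, SAP 8.5.2 (Singulex) plans "Graphical and tabular summaries of the distributions of VRC01/LS mucosal levels normalized by total IgG/protein", the same without normalization, and then "Correlation plots will be generated between different sample types". The planned outputs are:

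- **Tables (SAP 10.2.1).** Three sets of summary statistics, for example "VRC01/LS concentration normalized by total IgG and protein, by tissue type, visit, and treatment arm". None is split by sex at birth.
- **Graphs (SAP 10.2.2).** Boxplots of baseline levels and line plots over time, both split by sex at birth, plus correlation scatterplots such as "Rectal homogenates to Cervical lysates".

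On who supplies which sample, Protocol 9.6 says "At the Seattle CRS, female participants will also provide rectal fluids and rectal biopsies, if they agree to do so". Men give rectal tissue. Women give cervical and vaginal tissue, and a woman who stops cervicovaginal sampling may switch to rectal sampling.

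**The concern.** A same-participant comparison of levels needs a paired quantity: a ratio or difference per person, summarised with an interval. Neither type of planned level output supplies one. A correlation shows whether people who are high in one tissue are high in another; it does not show which tissue is higher. Summaries by tissue describe each compartment separately and leave out the within-person link.

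Three things follow. A high correlation could be misread as similar levels. In the tables, a mixed-sex rectal row stands beside women-only cervical and vaginal rows, with no interval for the difference. And cervix against vagina, the one pair that women at every site can provide, receives neither a contrast nor a scatterplot.

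**Working it through.** **1. The plan's own level calculation concerns correlation.** Protocol Table 6-3 uses Z' = arctanh(ρ) + ρ/(2(n−1)) with standard error 1/√(n−3), two-sided 0.05. For n = 11 and ρ = 0.6: Z' = 0.693 + 0.030 = 0.723; 0.723 × √8 = 2.045; 2.045 − 1.960 = 0.085; power = Φ(0.085) = 53%, as tabulated. All 49 cells reproduce, with a largest difference of 0.7 points. The documents give no figure for a contrast between mucosal compartments.

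**2. A correlation ignores scale.** On the log scale, multiplying one compartment by c adds ln c to every value. That leaves r unchanged and multiplies the paired geometric mean ratio by c. In one simulated sample of 22 pairs:

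| c | r | paired ratio |
|---|---|---|
| 1 | 0.56 | 0.88 |
| 2 | 0.56 | 1.76 |
| 5 | 0.56 | 4.40 |
| 10 | 0.56 | 8.79 |

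**3. The tables cannot be turned into a paired interval.** The variance of a within-person difference is s₁² + s₂² − 2ρs₁s₂. SAP 10.2.1 gives each tissue's SD but no within-person correlation, and gives arithmetic means rather than geometric ones. For cervical against vaginal tissue, no planned level display shows that correlation either.

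**4. Make-up of a rectal row.** Groups 1 and 2 each plan 10 men and 13 women (Protocol 6.1). If k women contribute rectal samples, with k not stated and between 0 and 13, the male share is 10/(10+k): from 10/23 = 43% to 10/10 = 100%.

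**5. What a paired analysis could deliver (illustration).** Applying the Protocol's 15% missing-data allowance gives 13 × 0.85 = 11 women per group. The documents give no mucosal SD or within-woman correlation, so both are assumed. The 95% CI multiplies and divides the geometric mean ratio by:

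- paired: exp[t₁₀ × s√(2(1−ρ))/√11], t₁₀ = 2.228
- unpaired: exp[t₂₀ × s√(2/11)], t₂₀ = 2.086

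For s = 1.0 and ρ = 0.6, paired: 2.228 × 0.894/3.317 = 0.601, and exp(0.601) = 1.82. Unpaired: 2.086 × 0.426 = 0.889, and exp(0.889) = 2.43.

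| ln-scale SD | paired, ρ=0.3 | paired, ρ=0.6 | paired, ρ=0.9 | unpaired |
|---|---|---|---|---|
| 0.5 | 1.49 | 1.35 | 1.16 | 1.56 |
| 1.0 | 2.21 | 1.82 | 1.35 | 2.43 |
| 1.5 | 3.29 | 2.46 | 1.57 | 3.80 |

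The SAP plans no unpaired interval. That column shows only what discarding the pairing would cost.

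**The case against.** The strongest reply is that this is one of nine exploratory objectives in a phase 1 trial. SAP 8.1 describes the analysis variables as those for primary and secondary objectives, and exploratory objectives 3 and 5 have no listed outputs either. SAP 8.5.1 also allows optional mixed models for drug levels. This stands as a limit on priority. It does not remove the gap: the SAP restates objective 4 and specifies its infectivity half, and the optional models are described for combining timepoints and for predicting mucosal levels from serum.

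A reader might also infer more than the documents support:

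- **That relative levels are never shown.** Per-tissue means and medians are tabulated, and cervical and vaginal rows come largely from the same women, so that comparison has no sex confounding. With complete pairs, the difference in means equals the mean paired difference. What is missing is a log-scale ratio and an interval.
- **That compartment is confounded with sex throughout, because rectal rows are mostly male.** A male majority is not established: the share runs from 43% to 100%, and women may switch to rectal sampling. The boxplots and line plots are split by sex, so the mixing is confined to the tables.
- **That the pairing is ignored.** The rectal-against-genital scatterplots use same-participant pairs, and the plotted points show both levels. They lack a numerical summary.
- **That comparing compartments is the main reason for the biopsies.** Protocol 4.4 asks what concentration reaches mucosal sites, how fast it decays and whether it is functional. Protocol 6.1.2 puts serum–mucosa correlation first.

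**Conclusion.** The point holds as a gap in the specification of one exploratory objective. The listed outputs, carried out exactly, produce no within-participant level ratio, difference or interval between cervix, vagina and rectum. This rests on reading the level outputs in SAP 8.5.1, 8.5.2, 10.2.1 and 10.2.2, and not on any assumed value.

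The interval widths are illustrative. At 11 pairs, the paired factor runs from 1.16 to 3.29 across the assumed SDs and correlations, so the cervical:vaginal ratio could be estimated usefully in some settings and only roughly in others. Rectal-against-genital ratios will have fewer pairs, because mainly consenting Seattle women give both; that number is not stated. SAP 8.5.2 says measured concentrations carry an unknown processing dilution and are not physiological, so any ratio should be read on a normalized scale. The primary serum-versus-mucosa objective and the safety analyses are unaffected.

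**What to change.** Add one exploratory table to SAP 8.5.2 and 10.2.1, by arm and visit, of within-participant geometric mean ratios with 95% CIs from paired log values. A mixed model with a participant random intercept, combining visits, is an alternative. Cover:

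- cervical:vaginal tissue, in all women with both samples;
- rectal:cervical tissue, rectal:vaginal tissue and rectal:cervicovaginal secretions, in women who gave both.

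Report the IgG-normalized and protein-normalized scales side by side, since they could rank compartments differently. Give the number of pairs in each cell. State a rule for values below the Singulex LLoQ: the SAP defines that limit per run but gives no handling rule, and its 0.5 µg/mL substitution is written for the serum ELISA. The infectivity section is not a template for the method, because the tests it names are two-sample tests. Keep the existing scatterplots as support.

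The cost is SAP wording and one more table from samples already scheduled. The drawback is few pairs and wide intervals for the rectal-against-genital ratios, which the table should show plainly.
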